### 5.3.4 ALLERGIC/HYPERSENSITIVITY REACTIONS

*'Allergic/hypersensitivity reactions'* or *'cytokine release syndrome/acute infusion reaction'*, per CTCAE v5.0, are defined as AEs related to xisomab 3G3 with onset typically within hours from the start of the study drug infusion. Symptoms should be managed per institutional guidelines as appropriate (e.g., antihistamines, corticosteroids, NSAIDs, and IV fluids).

### 5.3.5 CONTRACEPTION

The study agent described within this protocol may have adverse effects on a fetus in utero. Non-pregnant, non-breast-feeding women of child-bearing potential may be enrolled if they are willing to use adequate methods of birth control (Refer to Appendix B) or are considered highly unlikely to conceive.

Highly unlikely to conceive women are defined as:

1. Surgically sterilized, or
2. Women will be considered post-menopausal if they have been amenorrheic for 12 months without an alternative medical cause. The following age-specific requirements apply:
  - a. Women <50 years of age would be considered post-menopausal if they have been amenorrheic for 12 months or more following cessation of exogenous hormonal treatments and if they have luteinizing hormone and follicle-stimulating hormone levels in the post-menopausal range for the institution or underwent surgical sterilization (bilateral oophorectomy or hysterectomy).
  - b. Women ≥50 years of age would be considered post-menopausal if they have been amenorrheic for 12 months or more following cessation of all exogenous hormonal treatments, had radiation-induced menopause with last menses >1 year ago, had chemotherapy-induced menopause with last menses >1 year ago, or underwent surgical sterilization (bilateral oophorectomy, bilateral salpingectomy or hysterectomy).
3. Not heterosexually active for the duration of the study.

Participants should be informed that taking the study medication may involve unknown risks to the fetus (unborn baby) if pregnancy were to occur during the study. In order to participate in the study individuals must adhere to the contraception requirement (described above) for the duration of the study and during the follow-up period defined in Section 7.6. If there is any question that a participant will not reliably comply with the requirements for contraception, they should not be entered into the study.

### 5.3.6 USE IN PREGNANCY

If a participant inadvertently becomes pregnant while on treatment with study agent, the study site will contact the participant at least monthly and document the participant's status until the pregnancy has been completed or terminated. The pregnancy will be recorded on the (e)CRF and reported by the Investigator to the IRB (refer to Section 7.6.4).

### 5.3.7 USE IN NURSING WOMEN

It is unknown whether study agent is excreted in human milk. Since many drugs are excreted in human milk, and because of the potential for serious adverse reactions in the nursing infant, participants who are breast-feeding are not eligible for enrollment.

## 5.4 PRECAUTIONARY AND PROHIBITED MEDICATIONS, TREATMENTS, AND PROCEDURES

Antithrombotic agents (Warfarin, heparin products, direct oral anticoagulants) should be avoided while on study (except for standard of care heparin/tPA flushes if required for catheter maintenance/occlusion). Elective invasive procedures should be delayed until completion of the initial 18 day drug efficacy evaluation period.

### 5.4.1 BLOOD DONATION

Participants must not donate blood during treatment with study drug and for 1 month following initial administration.

## 6. STUDY PROCEDURES/EVALUATIONS AND SCHEDULE OF EVENTS

All study visits and laboratory procedures, where possible, should be conducted as part of scheduled standard of care visits.

### 6.1 STUDY SPECIFIC PROCEDURES

#### 6.1.1 MEDICAL HISTORY

A medical history will be obtained by the investigator or qualified designee. In addition to collecting information on demographics, the medical history will include all active conditions, and any condition diagnosed within the prior 10 years that are considered to be clinically significant by the Investigator. Details regarding the participant's cancer will be recorded separately and not listed as medical history.

#### 6.1.2 DISEASE ASSESSMENT

The Investigator or qualified designee will obtain prior and current details regarding the participant's cancer.

#### 6.1.3 MEDICATION HISTORY

A complete medication history will be acquired concurrent with medical history.

#### 6.1.4 PHYSICAL EXAMINATION

Physical exams must be performed by a medically qualified individual such as a licensed physician, Physician's Assistant or advanced Registered Nurse Practitioner as local law permits. The physical exam at baseline should include a complete physical exam per institutional standards. All other physical exams after baseline will include an evaluation of any AEs, or any previously reported symptoms, or prior physical examination findings.

A physical examination may include evaluating: weight, general appearance, head, ears, eyes, nose, throat, neck, skin, cardiovascular system, respiratory system, gastrointestinal system, and nervous system. For the purposes of assessing CAT, physical exam should include assessment of participant arm pain and swelling or erythema in the same arm as the catheter.

A physical exam to be conducted: as part of screening visit; within 24hrs or day of single dose of study treatment; and at EOT. If screening visit occurs within 24hrs of study treatment administration, provider visit does not need to be repeated. All physical examinations will also include:

##### 6.1.4.1 Vital signs

Vitals to be collected include BP, HR, temperature, and oxygen saturation by pulse oximetry. Unless noted otherwise, vitals will be obtained during each study visit incorporating a physical exam. Significant findings that were present prior to the signature of the informed consent must be included in the Medical History (e)CRF page. Significant new findings that begin or worsen after beginning study treatment must be recorded on the Adverse Event (e)CRF page.

#### **6.1.4.2 Performance status**

Unless noted otherwise, ECOG status (per Appendix A) will be obtained during each study visit incorporating a physical exam.

#### **6.1.5 HEIGHT AND WEIGHT**

Weight must be collected on the day of enrollment.

#### **6.1.6 CATHETER PLACEMENT**

Placement of the PICC in participants will be performed according to institutional guidelines. Ultrasound may be used to guide the placement of the PICC, and may include use of local anesthetic. The specific type of PICC (e.g., single or double lumen, brand) will be determined by participants' treatment management team based on needs of their planned anticancer therapy.

Placement of indwelling central venous catheters in participants will be performed according to institutional guidelines. Ultrasound may be used to guide the placement of the indwelling catheter and may include use of local anesthetic. The specific type of indwelling catheter will be determined by participants' treatment management team based on needs of their planned anticancer therapy.

#### **6.1.7 RADIOGRAPHIC IMAGING ASSESSMENTS**

All diagnostic and treatment-associated imaging (e.g., MRI, CT, PET) will be performed as clinically indicated in accordance with institutional standards for managing a participant's cancer. Per institutional standards, the use of additional imaging modalities such as the use of contrast venography for assessing CAT or lumen patency is also permitted as clinically indicated. Findings from these studies may be collected.

#### **6.1.8 ULTRASOUND**

Per institutional standards, catheters are evaluated for possible CAT via venous duplex ultrasonography 14 ( $\pm 4$ ) days from time of catheter placement (which will be  $\pm 2$  days from administration of study agent). Venous duplex ultrasonography to occur as part of EOT visit, prior to provider visit. Assessment will include compression imaging of all the accessible portions of the internal jugular, innominate, subclavian, axillary, cephalic and basilic veins, as well as color Doppler of the internal jugular, subclavian and axillary veins. VTE will be diagnosed based on non-compressibility of a vein segment and/or abnormal color Doppler patterns. Whether the presence of CAT in a participant is symptomatic or asymptomatic at time of ultrasound evaluation will be noted in CRF as part of assessment.

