A total of 50 participants are planned for enrollment into this study. Eligibility will be confirmed prior to planned PICC line placement or indwelling central venous catheter placement. Eligible participants that are scheduled to have a catheter inserted as part of their planned anticancer therapy will be enrolled to receive xisomab 3G3. Within 48 hours of insertion of the PICC or indwelling catheter (i.e.  $\pm$  2 days) per institutional standards, participants will undergo IV placement and receive a single dose of xisomab 3G3. Standard procedures for catheter maintenance for sterility and patency will be performed each time the catheter is accessed for use including 10 to 20 ml of normal saline pulsatile flush before and after use and every 7 days in the outpatient setting. Two days after administration of xisomab 3G3 participants may proceed with planned, standard-of-care anticancer treatment in consultation with their treating physician and in accordance with institutional guidelines. The **primary objective** is to measure the efficacy of xisomab 3G3, as determined by the incidence of ultrasound-confirmed CAT (both symptomatic and asymptomatic) within 18 days after catheter insertion, compared to historical cancer controls. All participants will undergo duplex venous ultrasound and physical examination to evaluate symptomatic or asymptomatic CAT at 14 ( $\pm$  4) days after catheter placement. If participants develop symptoms suggestive of CAT such as arm pain, swelling, or erythema in the arm with the PICC, those participants will undergo standard-of-care workup with a unilateral extremity duplex venous ultrasound in the affected arm or leg. Participants that have confirmed CAT or other thrombosis found on imaging, per investigator assessment, will be treated at the discretion of their treating physician per institutional guidelines and standards of care. The duplex venous ultrasound assessment will include evaluation of disease history and physical exam to further assess possible thrombosis-associated symptoms. The **secondary objective** is to establish the safety and tolerability of xisomab 3G3 administered near the time of central line placement in patients that are diagnosed with and treated for solid tumors. All participants will be followed for 60 days (or until resolution/stabilization of any clinically significant drug-related adverse event) from time of catheter insertion to assess for AEs and medication use.

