## 6.9 SCHEDULE OF EVENTS

Visit Days*	Screening**	On-Study Treatment	End of Treatment Visit Day 14 ( $\pm 4$ days)	Follow-Up Day 60 ( $\pm 4$ days)
	Days -28 to -3	Day 1		
Informed consent	X			
Inclusion/exclusion criteria	X			
Catheter placement A		X		
Xisomab 3G3		X		
Medical history	X			
Medication history	X			
Physical Examination C	X	X G	X	
Radiographic Imaging		Per investigator's discretion, as clinically indicated		
Ultrasound D			X	
Hematology	X			
Biochemistry	X			
Coagulation	X		X	
Pregnancy test E	X			
AE assessment and Conmeds B,F	X	X	X	X
Research blood draw/Assessment for Immunogenicity H	X	X	X	
Electrocardiogram I	X	As clinically indicated		

\* Ideally the clinic visit and all the study requirements should be performed as indicated.

\*\* Enrolled participants will receive a single fixed dose of xisomab 3G3 (2 mg/kg) through a peripheral IV or the inserted catheter within 48 hours of catheter placement (i.e.  $\pm 2$  days). If Xisomab 3G3 is administered prior to D1 catheter placement, eligibility must be confirmed prior to study drug administration.

A Placement of the catheter in participants will be performed according to institutional guidelines. Ultrasound may be used to guide the placement of the catheter, and may include use of local anesthetic.

B For concomitant medications – enter new medications started during the trial through the end of treatment visit.

C All physical exams will include assessing vital signs, weight and ECOG performance status.

D Per institutional standards, study participants will be evaluated for CAT via planned ultrasound 14  $\pm 4$  days after catheter insertion. Additional ultrasound evaluations may occur at any time during the study based on treating physician and PI discretion; however, only ultrasounds performed within 18 days from catheter placement will be included when computing CAT incidence. Ultrasound to occur as part of EOT, prior to provider visit.

E For women of reproductive potential, a serum pregnancy test should be performed within 3 days prior to first dose of trial treatment. Serum pregnancy test should be performed by the local study site laboratory per institutional guidelines, and repeated if required.

Visit Days*	Screening**	On-Study Treatment	End of Treatment Visit Day 14 ( $\pm 4$ days)	Follow-Up Day 60 ( $\pm 4$ days)

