#### 8.2.4 ANALYSIS OF THE EXPLORATORY ENDPOINTS

Descriptive statistics will be used to present results of coagulation measures (i.e., platelet count, PT/INR, and aPTT), drug PK, and incidence of catheter occlusion requiring medical therapy (specifically, local administration of tPA). The proportion of participants with symptomatic thrombosis by Day 18 and the median (and range) time from xisomab infusion to clot symptoms

will be reported for those (expected few) participants with symptomatic CAT. All exploratory endpoints will additionally be analyzed within each catheter type (i.e., PICC vs. indwelling central venous catheter).

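### The end-of-treatment scan precedes the provider visit that informs the symptomatic label, so that label can be set with a positive result known (minor; exploratory outputs only)

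*Combined protocol and SAP*

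**What the plan says.** - **Order of events.** Section 6.1.8: "Venous duplex ultrasonography to occur as part of EOT visit, prior to provider visit". Section 6.9, footnote D: "Ultrasound to occur as part of EOT, prior to provider visit".
- **What the provider visit is.** Section 6.1.4 uses the term for the visit that contains the physical examination: "If screening visit occurs within 24hrs of study treatment administration, provider visit does not need to be repeated". On who examines, it says: "Physical exams must be performed by a medically qualified individual such as a licensed physician, Physician's Assistant or advanced Registered Nurse Practitioner". A sonographer is not named.
- **Where symptoms are sought.** Section 6.1.4 puts the symptom check in that examination: "physical exam should include assessment of participant arm pain and swelling or erythema in the same arm as the catheter". Section 2.1 adds: "The duplex venous ultrasound assessment will include evaluation of disease history and physical exam to further assess possible thrombosis-associated symptoms". Section 6.5 likewise pairs the Day 14 scan with a history and examination.
- **What is recorded.** Sections 6.1.8 and 6.5 have symptomatic or asymptomatic status entered in the case report form. Section 6.1.8 asks for the status as it was when the scan was done. It does not say who records it, or whether that person knows the result.
- **Where the label is used.** Section 8.2.4 reports "The proportion of participants with symptomatic thrombosis by Day 18", and the median and range of time from infusion to clot symptoms. Both are exploratory (2.2.3). The primary analysis (8.2.2) counts symptomatic and asymptomatic CAT together.

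**The concern.** Arm pain is subjective, and mild swelling or redness depends on how hard one looks. An examiner who knows that a clot has been found may question and examine more closely. A participant who has been told of a clot may recall discomfort that would otherwise have gone unmentioned. Either would turn a clot found only by the scheduled scan into a symptomatic one. The onset date is exposed in the same way if it is first asked for after the result is known.

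The trial has a single arm, so no concurrent group carries the same error. Few symptomatic cases are expected, so a single changed label shows in the reported proportion. Symptom status before the scan also cannot be recovered later if it was not written down.

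**Working it through.** **Step 1: does the text allow the label to be set after the scan?**
- Sections 6.1.8 and 6.9 put the scan first and the provider visit second.
- Section 6.1.4 puts the check for arm pain, swelling and erythema in the provider's examination.
- Sections 2.1 and 6.5 tie history and examination to the assessment of thrombosis symptoms.
- No section masks the examiner, delays release of the result, or calls for a symptom record before the scan.

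So the plan, followed as written, permits a label set with the result known. It does not require one.

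**Step 2: which participants are exposed?** Participants who develop arm symptoms earlier are scanned because of them (2.1, 5.1), so their symptoms precede imaging. A negative scan cannot yield symptomatic CAT whatever symptoms are noted, since CAT requires a detected clot. That leaves participants with a positive scheduled scan whose symptoms are first elicited at the EOT visit, and one direction of error: from asymptomatic to symptomatic.

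**Step 3: is the primary analysis affected?** The plan's sample size was reproduced from section 8.3.1 (60% versus 40%, two-sided 0.05, 80% power, 4% ineligible), using the normal approximation for one proportion:
- n = [(1.96 × √(0.6 × 0.4) + 0.842 × √(0.4 × 0.6)) / 0.20]² = 47.09, rounded up to 48
- 48 / 0.96 = 50, which agrees with the plan. Approximate power at n = 48 is 0.807.

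Symptom status enters none of these inputs, and relabelling moves no case into or out of the pooled endpoint. Sample size, power and alpha stand.

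**Step 4: how sensitive are the exploratory outputs?**
- Evaluable participants: 50 × 0.96 = 48. Section 8.2.4 names no analysis set, so 48 is an assumption.
- Background symptomatic rate of 5–7% (1.1), used only for scale: 0.05 × 48 = 2.4 and 0.07 × 48 = 3.4, or about 3 cases.
- One relabelled case: 1/48 = 2.1 percentage points.
- 3/48 = 6.3% (exact 95% CI 1.3–17.2%) becomes 4/48 = 8.3% (2.3–20.0%).
- Time to symptoms: with three cases the median is the second value. A fourth case with onset at or after the third value moves the median to the midpoint of the second and third.

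**The case against.** The strongest reply is that little rests on this label. The endpoints that use it are exploratory and descriptive, and section 8.2.4 itself expects few symptomatic cases. A shift of 2 percentage points is small beside an interval running from 1.3% to 17.2%. The scan and the provider visit belong to the same EOT visit, so a careful history can still establish what was present before the scan. Adverse events are also to be reported throughout (6.1.9) with time of onset (7.5), which gives some symptoms an independent record. All of this stands, and it is why the point is minor. It does not close the gap for symptoms first elicited at the EOT visit.

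Several stronger readings are tempting, and the documents do not support them:
- **That the provider does know the result.** The documents do not say when the scan is read or reported. Only that the result can be known follows from the text.
- **That the primary result is biased.** The pooled endpoint ignores symptom status.
- **That symptoms discounted after a negative scan distort the symptomatic rate.** Such participants are not CAT cases.
- **That the rate would rise to a particular figure.** Taking 6% symptomatic and 40% total CAT in 48 participants leaves 19.2 − 2.9 = 16.3 clots found only by scan. Relabelling an assumed 10–20% of them gives about 9–13%. No document supports that share. The sum also joins a background symptomatic rate, which has no 18-day window and is not a rate on study drug, to the target total rate on treatment. The result lies inside the interval for 3/48 anyway.
- **That a planned historical comparison of symptomatic CAT fails.** None is planned. The 60% benchmark in 8.3.1 is for total CAT, and the 6.8% and 3.7% quoted in section 1.1 are background.

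**Conclusion.** The concern holds in a limited form. The stated order of scan and provider visit, with no symptom record before the scan, lets a positive result influence whether a clot is called symptomatic and what onset date is given. The reach is the symptomatic/asymptomatic split in the case report form and the two exploratory outputs in 8.2.4, for symptoms first elicited at the scheduled EOT visit. The size is about 2 percentage points per relabelled case, assuming 48 evaluable participants. The number of cases that would be relabelled cannot be estimated from the documents. The conclusion also assumes that the scan result can reach the examiner or participant before the history is taken, which the text neither states nor prevents. Severity: minor.

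**What to change.** In section 6.1.8 and footnote D of section 6.9, require that arm pain, swelling and erythema on the catheter side, with onset date, be recorded on a short checklist at the EOT visit before the scan is performed. State that this entry is the symptom status at the time of ultrasound for the case report form and for the 8.2.4 analyses. Do not give the checklist to the sonographer, so that it cannot influence the reading on which the primary endpoint depends. Leave the provider visit after the scan, so that the result is to hand there. Participants scanned earlier because of symptoms keep the status recorded at that workup.

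The cost is one short extra form at check-in and a sentence in each of the two sections. There is no added visit or procedure, and no change to sample size, power or the primary analysis. The change has to be made prospectively, because the status before the scan cannot be reconstructed for participants already assessed.

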#### **6.1.9 ADVERSE EVENT EVALUATION**

Toxicities and adverse experiences will be assessed at each visit using the [CTCAE v5.0](#).

Safety will be monitored by assessing physical examination, vital signs, and weight, performance status, hematology, chemistry, coagulation, and pregnancy, as well as collecting of the AEs and medications at study visits.

Adverse events will be monitored from the time the participant signs the informed consent form, but will not be included for analysis if occurring before the study agent is given. Participants will be instructed to report all AEs during the study and will be assessed for the occurrence of AEs throughout the study. All AEs (serious and non-serious) must be recorded in the medical record and (e)CRFs regardless of the assumption of a causal relationship with the study drug; however, known AEs associated with a participant's planned anticancer treatment regimen will not be collected except for the development of grade 3-4 thrombocytopenia. For details on AE collection and reporting, refer to Section 7, Safety.

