Primary Objectives	To evaluate the antithrombotic efficacy of prophylactic xisomab 3G3 treatment in cancer patients with a central venous catheter.

Secondary Objectives	To determine the safety and tolerability of prophylactic xisomab 3G3 treatment as measured by the incidence and severity of adverse events in cancer patients with a central venous catheter.
Exploratory Objective	Assessment of participant coagulation profiles, and the incidence of line occlusion requiring medical interventions to obtain patency.
Primary Endpoints	The number of participants with catheter-associated thrombosis, as defined by the total incidence of symptomatic and asymptomatic thrombosis, and thrombotic occlusion leading to device failure (start: administration of xisomab; end: Day 18)
Secondary Endpoints	The number of subjects with treatment-related adverse events (TRAEs) and treatment-emergent adverse events (TEAEs) will be summarized using frequency counts (start: time of consent, end: Day 60)
Exploratory Endpoints	Quantification of coagulation parameters and assessment of catheter occlusion (start: pre-dose, end: Day 18 [i.e., post-dose]): 
 
a. Activated partial thromboplastin time (aPTT)
 
b. Pharmacokinetic (PK) evaluation
 
c. Time to symptomatic catheter-associated thrombosis
 
d. Proportion of participants with a catheter occlusion requiring medical intervention
 

Number of Participants	
Duration of Therapy	1 day
Duration of Follow Up	60 days [post catheter placement]
Key Inclusion Criteria	
 
• Men and women, aged <math>\geq</math> 18 years and members of all races and ethnic groups will be included.
 
• Participants with any solid tumor malignancy that will undergo insertion of a central venous catheter (PICC or indwelling subclavian vein central venous catheter) as part of planned cancer-directed therapy per institutional standards
 
• Able to wait 1 day post-study drug infusion before receiving cancer-directed therapy.
 
• ECOG performance status <math>\leq</math> 2
 
• Expected life expectancy of <math>>6</math> months
 
• At time of enrollment, must have adequate platelet count (<math>>100 \times 10^9/L</math>)
 

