## 2.2.2 SECONDARY OBJECTIVES AND ENDPOINTS

Objective	Endpoint	Start	End
To evaluate the safety and tolerability of xisomab 3G3 in cancer patients with a PICC or indwelling catheter	
 
1. Incidence of major and clinically-relevant bleeding [refer to Section 6.1.9.1]
 
2. Incidence of xisomab 3G3-associated toxicities [per CTCAE v5.0]
 
	Administration of xisomab 3G3 (Day 1 ± 2 days)	End of follow-up (Day 60)

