## 6.4 SCREENING AND BASELINE ASSESSMENTS

A screening (consultation) visit may occur as part of standard of care. If a participant is eligible for the study after review of key inclusion/exclusion criteria, additional screening and/or baseline visits will be scheduled while staff members are requesting insurance authorization to participate in a clinical trial. The following will be reviewed at initial screening visit:

- Clinical history and physical exam (per standard of care)
- Informed consent obtained and documented

Toxicities which occur prior to the start of treatment will not be subject to analysis. Consent must be obtained before initiation of any clinical screening procedures that are performed solely for the purpose of determining eligibility for this research study. Evaluations performed as part of routine care before informed consent can be utilized as screening evaluations if done within the defined time period.

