### 8.1 ANALYSIS POPULATIONS

An intent to treat (ITT) analysis set consists of all participants who consent and enroll in the trial regardless of whether they are exposed to the study drug. An efficacy analysis set consists of participants who have placement of a catheter, receive xisomab 3G3 within 48 hours of catheter placement, and have at least one CAT assessment (i.e., ultrasound and physical exam) by Day 18 of the study. A safety analysis set consists of all participants who are exposed to the single dose of study drug.

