#### 8.2.3 ANALYSIS OF THE SECONDARY ENDPOINTS

The incidence of major or clinically relevant non-major bleeding (defined in Section 6.1.9.1), along with 95% CI, will be assessed using the safety analysis set. The proportion of safety set participants with these bleeding events will also be separately estimated for each catheter type.

The incidence of xisomab 3G3-associated toxicities will be assessed using the safety analysis set. Descriptive statistics of safety will be presented using CTCAE v5.0. All on-study AEs (from time of consent), treatment-related AEx (from time of xisomab infusion), SAEs, and treatment-related SAEs will be tabulated using worst grade per NCI CTCAE v5.0 criteria by system organ class and preferred term. On-study abnormal lab parameters including hematology, chemistry, liver function, and renal function will be summarized using worst grade NCI CTCAE v5.0 criteria.

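### The safety analysis starts at dosing in Sections 2.2.2, 6.1.9 and 6.4 but at consent in the Synopsis and, for all on-study AEs, in 8.2.3; treatment-emergent is undefined, so the Synopsis count can include subjects whose only event preceded the drug

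*Combined protocol and SAP*

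**What the plan says.** Three places start the safety analysis at dosing:

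- Section 6.1.9 separates monitoring, which begins at consent, from analysis: AEs "will not be included for analysis if occurring before the study agent is given".
- Section 6.4: "Toxicities which occur prior to the start of treatment will not be subject to analysis".
- Section 2.2.2 gives the start of both safety endpoints (bleeding and xisomab-associated toxicities) as "Administration of xisomab 3G3 (Day 1 ± 2 days").

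Two places start it at consent:

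- The Synopsis, under Secondary Endpoints, names "The number of subjects with treatment-related adverse events (TRAEs) and treatment-emergent adverse events (TEAEs") and says that they "will be summarized using frequency counts (start: time of consent, end: Day 60").
- Section 8.2.3: "All on-study AEs (from time of consent), treatment-related AEx (from time of xisomab infusion), SAEs, and treatment-related SAEs will be tabulated". All on-study AEs run from consent and treatment-related AEs from infusion. No start is attached to SAEs.

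Two further places bear on the question without settling it. Section 8.1 defines the safety set: "A safety analysis set consists of all participants who are exposed to the single dose of study drug". Section 7.5 records events from consent, collects time of onset and changes in severity, and treats conditions present at screening as baseline.

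**The concern.** An event with onset before the drug cannot have emerged on it. If the Synopsis window is followed literally, an illness between consent and dosing makes the subject a treatment-emergent case. The trial is single-arm, so no control group shows how many such events are background, and safety is its only secondary objective.

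The conflict also leaves a choice open at the analysis stage. An analyst following 8.2.3 would tabulate events that 6.1.9 and 6.4 say are not analysed, and an analyst following 6.1.9 would leave them out. The Synopsis and 8.2.3 also disagree with each other on treatment-related AEs, which start at consent in one and at infusion in the other. Two safety tables could be produced from the same data, each with support in the protocol.

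**Working it through.** **Side by side.** The plan states no figure here to reproduce, so the check is mainly a comparison of windows.

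| Place | What is counted | Start |
|---|---|---|
| Synopsis | Subjects with TRAEs and TEAEs | Consent |
| 2.2.2 | Bleeding; xisomab-associated toxicities | Administration |
| 6.1.9 | AEs included for analysis | Administration |
| 6.4 | Toxicities subject to analysis | Start of treatment |
| 8.2.3 | All on-study AEs | Consent |
| 8.2.3 | Treatment-related AEs | Infusion |
| 8.2.3 | SAEs | Not stated |

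**Does any other text resolve it?** TEAE has no definition in the protocol, and the only window attached to it is the one in the Synopsis. The safety set in 8.1 selects participants who were dosed; it sets no onset cut-off for their events. The baseline rule in 7.5 removes conditions already present at screening, but not events that begin or worsen between screening and dosing. Those events will be in the database.

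**Share of the window that is pre-drug.** Inputs: screening lasts up to 28 days before catheter placement (3.5), and follow-up is 60 days from placement (2.1, 6.7). With dosing taken as the day of placement:

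- share = pre / (pre + post)
- 28 / (28 + 60) = 28/88 = 32%
- 14 / (14 + 60) = 14/74 = 19%
- 3 / (3 + 60) = 3/63 = 5%

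If dosing falls 2 days after placement following a full 28-day screening, the share is 30/88 = 34%. Section 5.1 limits rescheduling to 28 days from consent, so about 32% is the practical maximum.

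**From days to subjects.** The Synopsis counts subjects, and a subject with events both before and after dosing counts once. As an illustration, assume a constant Poisson rate per subject, 60 post-dose days and 28 pre-dose days. If p is the proportion with at least one post-dose event, the proportion over the whole window is 1 − (1 − p)^(88/60).

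- p = 44%: 1 − 0.56^1.467 = 57%, a relative increase of 30%
- p = 80%: 1 − 0.20^1.467 = 91%, an increase of 13%
- p = 95%: 1 − 0.05^1.467 = 99%, an increase of 4%

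With 7 pre-dose days and p = 80%: 1 − 0.20^(67/60) = 83%, an increase of about 4%.

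The count of events would rise by 28/60 = 47% under the same assumptions. The count of subjects approaches that figure only when events are rare. The values of p are illustrative. The protocol gives neither a background AE rate for this population nor an expected screening duration.

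**The case against.** The best defence is that the Synopsis gives a collection window. Section 6.1.9 draws that distinction, 7.5 also records from consent, and the usual meaning of treatment-emergent excludes pre-dose events. This is plausible, but the Synopsis attaches its window to the summary of the endpoint, and no definition overrides it. Nor does this reading help 8.2.3, which is an analysis section and tabulates from consent.

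Other limits on the point stand:

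- A reader might infer that 8.2.3 plans treatment-emergent tables contaminated by pre-dose events. It does not. It never uses the term, labels its from-consent table as all on-study AEs, and starts treatment-related AEs at infusion.
- A reader might take 32%, or 47%, as the inflation of the endpoint. The first is a maximum share of calendar time and the second an event-count figure; the endpoint counts subjects. A constant rate is also doubtful: the catheter and the anticancer treatment come around or after dosing, which could raise the post-dose rate and shrink the pre-drug share.
- A reader might infer that many catheter complications would be charged to the drug. Dosing is within 48 hours of placement on either side, so pre-drug events from the study catheter can arise in at most about 2 days, and in none if dosing comes first.
- Bleeding, the only safety outcome for which 8.2.3 plans a confidence interval, starts at administration in 2.2.2, and no text starts it at consent.
- No hypothesis test depends on the AE counts, and the pause rules in 7.7 turn on attributable or suspected-related events.

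**Conclusion.** The inconsistency is real and present in the current text. The five places cannot all be followed. As written, the Synopsis endpoint can count subjects whose only event preceded the drug. The conflict in 8.2.3 is over whether pre-dose AEs are analysed at all, together with its disagreement with the Synopsis on when treatment-related AEs start.

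The size cannot be computed from the documents. The firm statement is that at most about 32% of the consent-to-Day-60 window is pre-drug. The move from 80% to about 91% of subjects is an illustration that rests on a constant Poisson rate and a full 28-day screening for everyone; shorter screening gives much less. The documents do not support a claim that the bleeding estimate, a test or a stopping decision would change. This is a wording fault of modest consequence. It deserves correction before analysis because the trial has no control arm and the choice of table should not be made after the data are seen.

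**What to change.** 1. **Synopsis, Secondary Endpoints:** change the start of the TRAE and TEAE endpoint to xisomab administration, and define a TEAE as an event with onset or worsening at or after administration.
2. **Section 8.2.3:** tabulate AEs and SAEs with onset or worsening at or after administration, and list events between consent and dosing separately. This agrees with 2.2.2, 6.1.9 and 6.4 and gives SAEs the start that they now lack.
3. **End of the window:** state one. Section 6.7 follows participants to 60 days from catheter placement, while 7.5 records events to 60 days after the dose. With dosing up to 2 days either side of placement, the two ends can differ by up to 2 days and should be reconciled.

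The cost is wording only. Time of onset and changes in severity are already collected under 7.5, so no new data, visits or participants are needed.
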